Proprietary confidential information			
© 2017 Boehringer Ingelheim International GmbH or one or more of its affiliated companies. All rights reserved.			
This document may not - in full or in part - be passed on, reproduced, published or otherwise used without prior written permission			
Research question and objectives:	
Primary: To assess the effectiveness of maintenance treatment of COPD with the combination of the LAMA tiotropium with a LABA compared with the combination of a LABA with ICS on the time to COPD exacerbation.
 
Secondary: To compare the effectiveness on the rate of exacerbation and the safety on the incidence of community acquired pneumonia for LABA and tiotropium with LABA and ICS.
		
Study design:	
A prevalent new-user cohort design will be used, with time-conditional propensity scores to match the two comparison groups.
		
Population:	
The base cohort will consist of all patients with a diagnosis of COPD who received at least one prescription for a long-acting bronchodilator, either LABA or the LAMA tiotropium, or for an inhaled corticosteroid from 1 January 2002 until 31 December 2015. To increase the likelihood of a diagnosis of COPD, we only include patients 55 years of age or older on the date of this initial prescription and exclude all patients with a prior diagnosis of asthma.
 
The primary study cohort will first be defined as the members of the base cohort with their first concurrent prescriptions of a LABA and tiotropium on the same date. Patients initiating a LABA and tiotropium will not include users of a LABA+ICS fixed dose combined inhaler.
 
Patients receiving for the first time a LABA and tiotropium on the same day will be propensity score and time matched with members of the base cohort who initiate treatment with LABA and ICS on the same day, either as a fixed-dose combination or free combination.
 
Subjects will need to have at least one year of medical history information prior to the date of combined treatment initiation (cohort entry date) to allow the identification of new use and the measurement of baseline covariates. Subjects will be followed for up to one year from the date of combined treatment initiation, or until switching to the other treatment, the date of death, 31 December 2016, or the end of coverage in the practice, whichever occurs first.
		

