Study data source:	
United Kingdom's Clinical Practice Research Datalink (CPRD) linked with the Hospital Episodes Statistics (HES) database
		
Expected study size:	
New users of LABA and tiotropium : 3,000
 
New users of LABA and ICS: 3,000
		
Main criteria for inclusion:	
 - New users of long-acting bronchodilators, LABA and tiotropium on the same date or of LABA and ICS, either as a fixed-dose combination or free combination, on the same date between January 2002 and December 2015. - Diagnosis of COPD and age \geq 55 years 		

Name of company: Boehringer Ingelheim		 Boehringer Ingelheim	
Name of product: Spiriva			
Name of active ingredient: Tiotropium bromide			
Protocol date: 19 May 2017	Study number: 0205-0538	Version/Revision: 1.1	Version/Revision date: Version 1.1, May 19, 2017

Proprietary confidential information © 2017 Boehringer Ingelheim International GmbH or one or more of its affiliated companies. All rights reserved. This document may not - in full or in part - be passed on, reproduced, published or otherwise used without prior written permission
			
Main criteria for exclusion:	-Less than one year of medical history information prior to the date of combined treatment initiation (cohort entry) -Asthma diagnosis		
Comparison groups:	Initiating LABA and tiotropium compared to initiating LABA and ICS therapy		
Expected duration of exposure:	One year for the primary and secondary analyses		

TABLE OF CONTENTS

TITLE PAGE	1
PROTOCOL ABSTRACT	3
TABLE OF CONTENTS	6
LIST OF TABLES	8
LIST OF FIGURES	9
1. LIST OF ABBREVIATIONS AND TERMS	10
2. RESPONSIBLE PARTIES	11
3. AMENDMENTS AND UPDATES	12
4. MILESTONES	13
5. RATIONALE AND BACKGROUND	14
6. RESEARCH QUESTIONS AND OBJECTIVES	15
7. RESEARCH METHODS	16
7.1 STUDY DESIGN.....	16
7.2 SETTING.....	16
7.3 SUBJECTS	16
7.4 VARIABLES	17
7.4.1 EXPOSURES.....	17
7.4.2 OUTCOME(S).....	17
7.4.2.1 PRIMARY OUTCOME(S).....	17
7.4.2.2 SECONDARY OUTCOME(S).....	18
.....	18
7.4.3 COVARIATES.....	18
7.5 DATA SOURCES	19
7.6 BIAS	19
7.7 STUDY SIZE	19
7.8 DATA MANAGEMENT	20
7.9 DATA ANALYSIS	20
7.9.1 MAIN ANALYSIS	20
.....	21
7.10 QUALITY CONTROL.....	22
7.11 LIMITATIONS OF THE RESEARCH METHODS	22
7.12 OTHER ASPECTS	22
8. PROTECTION OF HUMAN SUBJECTS	23
9. MANAGEMENT AND REPORTING OF ADVERSE EVENTS/ADVERSE REACTIONS.....	24
10. PLANS FOR DISSEMINATING AND COMMUNICATING STUDY RESULTS	25
11. REFERENCES.....	26

11.1	PUBLISHED REFERENCES.....	26

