6. RESEARCH QUESTIONS AND OBJECTIVES

The primary objective of this study is to assess the effectiveness of maintenance treatment of COPD with the combination of a LABA and the LAMA tiotropium (LABA-TIO) compared with the combination of a LABA and an ICS (LABA-ICS) on the time to COPD exacerbation. More specifically, the patients who initiate treatment with a combination of a LABA and tiotropium at the same time, or who are on a LABA (no ICS) and who add tiotropium, or who are on tiotropium and add a LABA (no ICS), will be compared with similar patients who receive a LABA and an ICS on the time to first COPD exacerbation.

The secondary objective is to assess the comparative effectiveness on the rate of exacerbation and the comparative safety on the incidence of community acquired pneumonia.

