The study cohort will be formed from the base cohort using an incident new-user cohort design with time-conditional propensity scores [P17-04653]. We will thus identify from the base cohort all subjects who, during follow-up, received for the first time prescriptions for a LABA and a tiotropium on the same day, but no inhaled corticosteroid. This can occur as the first time they received a long-acting bronchodilator, with both a LABA and tiotropium as initial treatment, or with initial treatment with a single long-acting bronchodilator followed by the addition of the other long-acting bronchodilator. We will then identify from the base cohort all subjects who, during follow-up, received for the first time prescriptions for a LABA and an ICS on the same day, as two different prescriptions or in a single inhaler, but no tiotropium. Here again, this can occur as the first time they received a LABA and ICS as initial treatment, or with initial treatment with a LABA followed by the addition of ICS or vice versa. Cohort entry will be taken as the first date that LABA and tiotropium or LABA and ICS prescriptions are given simultaneously. All subjects will require at least one year of up-to-standard (UTS) medical history prior to study cohort entry to allow a baseline period for the covariates and identification of new use. New use will thus be defined as the first simultaneous prescriptions for LABA and tiotropium or for LABA and ICS, preceded by prescriptions for only one of the two drug classes or none in the baseline year.

To form the study cohort, we will identify, for each subject initiating LABA and tiotropium (LABA-TIO) treatment, a matched LABA-ICS comparator subject using a time-conditional

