7.7 STUDY SIZE

In our previous study of the cardiovascular effects of long-acting bronchodilators, there were around 230,000 users of LABA or TIO between 2002 and 2012 in the CPRD, which should include around 140,000 who come from HES-linked practices [P16-10095]. From these, we expect around 4,000 who received a LABA and tiotropium on the same day, where the LABA is not combined with an inhaled corticosteroid in a single inhaler. The number of users of LABA-ICS is over 100,000, providing a large pool for matching purposes. Thus, after matching and trimming, we expect the study to include a minimum of 3,000 patients per arm, a conservative estimate. Using recent data from the FLAME trial [P16-05628], we expect that the cumulative incidence of a first COPD exacerbation, moderate or severe,

during the one-year follow-up is expected to be 50%. These sample sizes will permit to detect a 15% reduction in the risk of a first exacerbation (hazard ratio 0.85) with 99% power and a 10% reduction (hazard ratio 0.90) with 97% power. For the severe exacerbations, we expect the one-year cumulative incidence to be around 15%, which will permit to detect a 20% reduction in the risk of a first severe exacerbation (hazard ratio 0.80) with 92% power.

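### Do the looser third-drug wordings in the abstract and section 7.7 leave membership of the two arms open, given the stricter entry rule in section 7.3?

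*Combined protocol and SAP*

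**What the plan says.** Section 7.3 (Study Cohort) sets the entry rule for both arms. LABA-TIO patients are those who "received for the first time prescriptions for a LABA and a tiotropium on the same day, but no inhaled corticosteroid". LABA-ICS patients receive their two drugs "on the same day, as two different prescriptions or in a single inhaler, but no tiotropium". Section 6 repeats the no-ICS condition for the add-on routes into LABA-TIO.

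Two other places are worded more loosely:

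- **Abstract, Population:** "Patients initiating a LABA and tiotropium will not include users of a LABA+ICS fixed dose combined inhaler". The comparators are "members of the base cohort who initiate treatment with LABA and ICS on the same day, either as a fixed-dose combination or free combination", with no mention of tiotropium. The abstract's inclusion and exclusion criteria add no third-drug condition.
- **Section 7.7:** the expected 4,000 LABA-TIO patients are those "where the LABA is not combined with an inhaled corticosteroid in a single inhaler".

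On routes of entry, 7.3 says LABA-ICS may begin with both drugs together or "with initial treatment with a LABA followed by the addition of ICS or vice versa". It then matches exactly on prior treatment, with levels for LABA only, tiotropium only, ICS alone and none. Follow-up ends when an ICS is added in LABA-TIO or tiotropium is added in LABA-ICS.

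**The concern.** The abstract does state an ICS restriction, and it is narrower than the one in 7.3. If the abstract were programmed, some LABA-TIO patients would be on an ICS from day one and some LABA-ICS patients on tiotropium. That would blur the exacerbation contrast and, more so, the pneumonia contrast. If 7.3 is programmed, the 4,000 behind the study size may include ineligible patients.

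There is also a smaller point. Tiotropium-first patients can enter LABA-TIO and must be matched to LABA-ICS patients with prior tiotropium only, yet no listed LABA-ICS route starts from tiotropium. Nor does 7.3 say what happens when an exact-match stratum has no comparator; its fallback relaxes only the propensity score.

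**Working it through.** **1. The rules side by side, by prescriptions on the entry date**

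| Prescribed that day | Section 7.3 | Abstract | 7.7 count |
|---|---|---|---|
| LABA + tiotropium | LABA-TIO | LABA-TIO | counted |
| LABA + ICS (either form) | LABA-ICS | LABA-ICS | – |
| LABA + tiotropium + separate ICS | neither | both | not removed |
| LABA/ICS inhaler + tiotropium | neither | LABA-ICS | not counted |

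Read at the entry date, everyone in a 7.3 arm is in the same arm under the abstract. The abstract is looser and does not conflict on who belongs. In the third row it puts one patient in both arms and offers no tie-break, so it cannot serve as the working definition; 7.3 can. The follow-up rule points the same way: adding the third drug is a stopping event only if that drug was absent at entry.

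**2. Study size**

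Inputs from 7.7: 4,000 before matching, at least 3,000 per arm after, 50% incidence, ratio 0.90, stated power 97%. A two-sided 5% level is assumed, from the 95% confidence intervals in 7.9.1.

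The plan's figure is reproduced by comparing two proportions, 50% and 45%:

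power = Φ(0.05 / √[(0.50×0.50 + 0.45×0.55)/3,000] − 1.96) = Φ(3.883 − 1.96) = 97.3%.

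The documents do not give the share *t* with a separate ICS inhaler, so 5–15% is assumed:

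- Eligible pool 4,000 × (1 − t): 3,800 at 5%, 3,400 at 15%.
- Step already allowed for in 7.7: 3,000/4,000 = 75% retained.
- Retention needed to keep 3,000: 3,000/3,800 = 78.9%; 3,000/3,400 = 88.2%.
- If 75% retention applied regardless: 2,850 to 2,550 per arm, with power 96.6% to 94.7%.

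Treating 0.90 as a true hazard ratio gives Φ(√(2,892/4) × |ln 0.90| − 1.96) = 80.9% at 3,000 per arm, and 78.9% to 74.3% at 2,850 to 2,550. The drop from 97.3% to 80.9% is a separate matter (risk ratio versus hazard ratio) and is there whatever the entry rule.

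**3. Bias, only if the abstract were programmed instead of 7.3**

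Assume an exacerbation rate ratio of 0.8 for three drugs and a true pneumonia HR of 0.70. Neither figure is in the documents.

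- Exacerbation, true HR 1.00, only LABA-TIO contaminated: 1 − 0.2t = 0.99 to 0.97.
- Exacerbation, equal shares in both arms: (1 − 0.2t)/(1 − 0.2t) = 1.00. The abstract leaves both arms open, so one-arm contamination is not the natural case.
- Pneumonia: 0.70(1 − t) + 1.00t = 0.715 to 0.745.

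**4. The tiotropium-first route**

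In 7.3 the no-tiotropium phrase qualifies the prescriptions issued on the entry day. The new-use sentence limits only the arm's own two classes. With a tiotropium-only matching level, the coherent reading admits prior tiotropium users to LABA-ICS and stops follow-up at any later tiotropium prescription.

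Left-over supply could then overlap with early follow-up, for under 60 days on the plan's current-use window. Assume 30 days' overlap, tiotropium-first share *s*, follow-up *F* and the same 0.8:

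- If every such patient is censored at 30 days, the three-drug share of person-time is c = 30s/(30s + (1 − s)F). For s = 0.05, F = 365: c = 0.4%, HR = 1/(1 − 0.2c) = 1.001. For s = 0.60, F = 180: c = 20%, HR = 1.042.
- If they stay on LABA-ICS like the others, c = 30s/F. For s = 0.60, F = 180: c = 10%, HR = 1.02.

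**The case for a change.** The best case for acting is that the abstract does more than omit detail. It states a restriction, the restriction is too narrow, and 7.7 repeats it in the main body to define the count that supports the study size. The abstract also recognises LABA and ICS given as a "free combination" in effect, since it accepts them in separate inhalers, so a separate ICS inhaler is no remote case. The follow-up rule would not remove a third drug already present at entry. Arm membership, on this view, should read the same everywhere before programming.

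Part of this stands. The wordings differ, and 7.7 does not say whether its 4,000 leaves out patients with a separate ICS inhaler. Section 7.3 does not list the tiotropium-first route into LABA-ICS or the mirror case, ICS-first into LABA-TIO, although both are matching levels. It also does not say whether a repeat of an earlier third drug counts as an addition, or what happens in an empty stratum.

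These gaps are ones an analyst fills in the obvious way: follow the methods section, treat any third-drug prescription after entry as an addition, and leave a patient with no exact-match comparator unmatched. Section 7.7 already expects losses in matching and trimming and cites over 100,000 LABA-ICS users as the pool, though it gives no stratum sizes. Section 7.9.1 already promises baseline characteristics for the unmatched and matched cohorts.

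**Conclusion.** No change to the plan is needed. The abstract is a loose synopsis of a rule that 7.3 states in full, and harm would require programming the synopsis over the methods section. The 7.7 figure is an approximate count. An assumed 5–15% reduction leaves 3,800–3,400 patients, so 3,000 per arm is out of reach on this ground alone only if the share exceeds 25% (1 − 3,000/4,000). The source count also covers 2002 to 2012 while entry runs to the end of 2015, which may add to the pool.

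Under 7.3 as written, the only exposure overlap left is in the tiotropium-first stratum: an HR shift from 1.00 to at most about 1.02–1.04 at an assumed 60% share, and close to nil at 5%. All these sizes rest on assumed shares and rate ratios, because the documents give none. At a zero share of separate ICS inhalers the entry-rule effect vanishes. No figure stated in the plan is shown to be wrong by this point.

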7.3 SUBJECTS

The base cohort will consist of all patients with a diagnosis of COPD from 1 January 1995 until 31 December 2015 who subsequently received at least one prescription for a long-acting bronchodilator, either LABA or tiotropium, or for an inhaled corticosteroid, alone or in combination, from 1 January 2002 until 31 December 2015. The time span for the study was selected to ensure that LABAs and tiotropium were concurrently available, in view of the differing dates of market entry for LABAs (1990s) and tiotropium (2002). To increase the likelihood of a diagnosis of COPD, we will exclude all patients less than 55 years of age on the date of their initial prescription for these drugs during this time period and exclude all patients with a previous diagnosis of asthma. Because the definition of some outcomes under study involve hospitalization, the base cohort will be restricted to the practices which can be linked to the Hospital Episodes Statistics (HES) database (please refer to section 7.5).

Study Cohort

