propensity score-matched approach. The potential comparator subjects will be selected from the base cohort by forming time-based exposure sets defined by the calendar year of entry into the base cohort for the LABA-TIO and LABA-ICS simultaneous prescription users. To allow matching on the propensity of treatment choice, we will compute high-dimensional time-conditional propensity scores (TCPS) by identifying all available data (e.g., diagnoses, procedures, medications) in the one-year period prior to the date of cohort entry for each time-based exposure set using Cox proportional hazards regression. Then, for each LABA-TIO exposed subject, and starting chronologically with the first one, we will identify a matched comparator subject from the members of the subject's time-based exposure set. We will first match subjects on sex, previous components of the study treatment (LABA only, TIO only, ICS alone, none of these) and the presence of an acute COPD exacerbation in the year before cohort entry. The matched reference subject will then be selected as the one with the closest time-conditional propensity score in the matched set, after trimming within each exposure set, and allowing a maximum difference in scores of 0.05 for a match. In the absence of a tight propensity score match, we will take the closest and the analysis will be complemented by an adjustment for the propensity score.

After matching, the subjects in the study cohort will be followed up for up to one year from cohort entry (the date of the matched set), with follow-up ending at the earliest of the date of a switch or addition of either an ICS for the LABA-TIO group or of tiotropium to the LABA-ICS group, death, one year after cohort entry, December 31, 2016, or the end of coverage in the practice, whichever occurs first.

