7.4.3 COVARIATES

Sex, previous treatment and previous acute COPD exacerbation, as well as calendar year of cohort entry, are all matching factors and will thus inherently be accounted for.

Although we will use the high-dimensional approach to identify variables entering the time-conditional propensity score, some key covariates will be highlighted. First, we will identify key lifestyle variables available in the CPRD, known to be risk factors and potential confounders, including the body mass index (BMI), smoking status and excessive alcohol consumption. Missing data for smoking status and BMI will be entered as an additional category in the model. We will also explore the possibility of obtaining blood eosinophils measured in the year prior to cohort entry and will use this information only if complete.

Second, the occurrence of the study outcomes prior to cohort entry will be identified during the one-year baseline period and adjusted for in the analysis if found to be imbalanced between treatment groups after propensity score matching. In particular, COPD exacerbations occurring in the 30 days prior to the study cohort entry date, a marker of COPD exacerbation risk, will be identified separately from those occurring previously during the baseline year. In addition, the severe exacerbations requiring hospitalizations will be counted, while the moderate exacerbations will be identified from counts of prescriptions for oral corticosteroids.

Third, use of other respiratory drugs during the baseline period will be included as a measure of COPD severity. Thus, the number of prescriptions for short-acting beta-agonists, anticholinergics, methylxanthines and muscarinic antagonists used during the year prior to cohort entry will be identified. As well, the number of prescriptions for antibiotics for a respiratory condition will be counted. In addition, we will count the number of prescriptions for the study drugs used during the baseline period. These will be combined into a single variable because of the study design which inherently selects patients into the two study groups according to their prior LABA, TIO or ICS use. Finally, for each of the cohorts, baseline co-morbidity will be measured using diagnoses and prescriptions for various conditions observed often in patients with COPD, namely cardiovascular disease, diabetes, thyroid disease, renal failure, autoimmune disease and cancer, all in the year prior to cohort entry.

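### Section 7.3 builds the matching sets on base-cohort entry year, so it does not guarantee the match on year of combination start that 7.4.3 says is already accounted for

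*Combined protocol and SAP*

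**What the plan says.** The protocol works with two cohorts.

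- **Base cohort (7.3).** Patients with COPD who "received at least one prescription for a long-acting bronchodilator, either LABA or tiotropium, or for an inhaled corticosteroid, alone or in combination" between 1 January 2002 and 31 December 2015. The section gives this qualifying prescription but never states an entry date.
- **Study cohort (7.3).** Here the date is explicit: "Cohort entry will be taken as the first date that LABA and tiotropium or LABA and ICS prescriptions are given simultaneously". The abstract agrees.

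The matching rule in 7.3 takes comparators from "time-based exposure sets defined by the calendar year of entry into the base cohort for the LABA-TIO and LABA-ICS simultaneous prescription users". Within a set, patients are matched on sex, previous study-treatment component and exacerbation in the prior year, and then on the time-conditional propensity score.

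Section 7.4.3 describes the result differently. Sex, previous treatment and previous exacerbation, "as well as calendar year of cohort entry, are all matching factors and will thus inherently be accounted for". Section 7.6 says only that calendar time is matched, without saying which date it means.

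The primary objective in section 6 includes step-up patients, those "who are on a LABA (no ICS) and who add tiotropium, or who are on tiotropium and add a LABA (no ICS"). Section 7.3 admits step-up patients to both arms.

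**The concern.** One section states the rule and another states a property that the rule does not guarantee. A programmer following 7.3 literally and one following 7.4.3 would build different matched cohorts whenever patients step up to the combination in a later year than their first study drug.

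The study is not randomised, and 7.11 places confounding by indication among its main threats. Matching is the principal defence. Entry may fall anywhere in a 14-year window. If outcome rates or prescribing habits change over that window, and if the delay before step-up differs between the arms, a mismatch in year of combination start could confound the comparison. Because 7.4.3 treats that year as settled by design, the plan names it neither as a covariate nor as a balance check.

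**Working it through.** The plan gives no figure to reproduce on this point. The check sets the dates side by side and works out what each matching key allows.

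**Inputs**
- A = year of base-cohort entry, read as the first LABA, tiotropium or ICS prescription (7.3; inferred).
- B = year of study-cohort entry, the first simultaneous prescriptions (7.3; stated).
- Both lie between 2002 and 2015 (7.3; abstract, main criteria for inclusion).

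**Step 1: relation between the dates.** A cannot be later than B. If the combination is the first study drug, A = B and there is no discrepancy. If a single component came first, A ≤ B ≤ 2015, and the years can differ.

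**Step 2: what the 7.3 key allows.** All members of a set share A. Their B can be any year from A to 2015, so the largest possible within-pair gap in B is 2015 − A.

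| Base-entry year A | Largest possible gap in year of combination start |
|---|---|
| 2002 | 2015 − 2002 = 13 |
| 2005 | 2015 − 2005 = 10 |
| 2010 | 2015 − 2010 = 5 |
| 2015 | 2015 − 2015 = 0 |

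Under the key that 7.4.3 describes, the gap in B is 0 in every row.

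**Step 3: a pair that 7.3 permits.** Two patients of the same sex and exacerbation history, both on a LABA alone, enter the base cohort in 2003. One adds tiotropium in 2004 and the other adds an ICS in 2014. They share an exposure set and all the exact matching factors. With close enough scores they can be paired, although they started their combinations 2014 − 2004 = 10 years apart.

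**Step 4: whether another stated step fixes B.**
- The exact matches (sex, previous component, prior exacerbation) do not involve B.
- The score's covariates are drawn from data "in the one-year period prior to the date of cohort entry for each time-based exposure set using Cox proportional hazards regression". Year of combination start is not named among them.
- For earlier study-drug use, 7.4.3 says "we will count the number of prescriptions for the study drugs used during the baseline period". That is a count within one year and does not date the first prescription.
- The outcome model in 7.9.1 adds score decile and characteristics that differ after matching. It does not name B.

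No stated step restores the match on B that 7.4.3 claims.

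**The case against.** The strongest reply is that this is a slip in one phrase. Base-cohort entry has no stated date, so the conflict depends on an inference. The phrase in 7.3 goes on to refer to simultaneous-prescription users, which could be read as entry in that capacity. The same section links the date of cohort entry to each exposure set ("in the one-year period prior to the date of cohort entry for each time-based exposure set using Cox proportional hazards regression") and says that subjects are "followed up for up to one year from cohort entry (the date of the matched set"). The abstract speaks of time matching. All of this points to study-cohort entry as the intended key. The reply stands as evidence of intent. It does not remove the problem, because 7.3 is the operative instruction and no step in it, read literally, produces a common date for the pair.

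A second reply is that 7.9.1 compares the groups after matching and adjusts for what differs. This stands in part: an imbalance would be corrected, but only if year of combination start is among the characteristics compared. Section 7.4.3 gives the analyst reason to leave it out.

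A reader might go further and infer that matched pairs will commonly be many years apart, or that the hazard ratio is biased. The documents do not support either. They give no share of step-up patients, no distribution of delay to step-up by arm, and no calendar trend in exacerbation or pneumonia rates.

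A reader might also count it as an error that time since first study drug is not a named adjustment, or that the time axis of the Cox score model is unstated. Elapsed time may enter through that axis. No section claims to match on elapsed time, however, so these are optional clarifications outside the contradiction.

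**Conclusion.** The inconsistency is real and should be resolved before matching is run. As written, 7.3 does not ensure that pairs share a calendar year of combination start, and 7.4.3 says that they do. The finding is confined to patients whose first study drug preceded the combination. The 13-year figure is a bound set by the entry window and is not an expected gap. The size and direction of any bias are unknown.

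The conclusion rests on one assumption: that base-cohort entry means the first qualifying prescription. If the authors meant study-cohort entry, the design is as 7.4.3 describes and only the wording of 7.3 is at fault.

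**What to change.** **Preferred.** In 7.3, define the exposure sets by calendar year of study-cohort entry, that is, the year of the first simultaneous prescriptions. This agrees with 7.4.3 and with the reference in 7.3 to a single date for each matched set.

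**If base-entry year is truly intended.** Keep it and state its date. Add calendar year of study-cohort entry to the matching or to the outcome model, and correct 7.4.3 so that it no longer says this year is matched by design.

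**In either case.** List calendar year of study-cohort entry among the characteristics compared in the matched cohort under 7.9.1, so that the existing rule on adjusting for differences can act on it. It would help to say in 7.6 which calendar time is meant.

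**Cost.** A few phrases, and one balance row or model term. Re-keying changes the composition of the sets, and some may be thinner. Section 7.7 expects over 100,000 LABA-ICS users, but that is a gross count and does not show supply within each set, so this should be checked once the sets are formed. The change is cheap now and would mean rebuilding the cohort if made after matching.

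### Time since COPD diagnosis is absent from the matching, the score and the listed covariates, and control of treatment duration depends on a calendar year and a time axis that the plan does not settle

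*Combined protocol and SAP*

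**What the plan says.** The base cohort (7.3) takes "all patients with a diagnosis of COPD from 1 January 1995 until 31 December 2015 who subsequently received at least one prescription" for a LABA, tiotropium or ICS between 2002 and 2015. Patients may enter the study cohort on both drugs at once or "with initial treatment with a single long-acting bronchodilator followed by the addition of the other long-acting bronchodilator"; the LABA-ICS side allows the same two routes.

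Comparators are found by "forming time-based exposure sets defined by the calendar year of entry into the base cohort". The score is then built "by identifying all available data (e.g., diagnoses, procedures, medications) in the one-year period prior to the date of cohort entry", and estimated "for each time-based exposure set using Cox proportional hazards regression". The exact-matching step reads "We will first match subjects on sex, previous components of the study treatment (LABA only, TIO only, ICS alone, none of these", and adds any acute exacerbation in the prior year. The score caliper is 0.05, with a fallback: "In the absence of a tight propensity score match, we will take the closest", plus adjustment for the score.

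Section 7.4.3 gives the calendar matching factor as the year of cohort entry, not base-cohort entry. It measures prior exacerbations, respiratory drugs, the study-drug prescription count and comorbidity over the baseline year. Section 7.6 says that general COPD severity is in the score and the outcome model. Section 7.9.1 adjusts the Cox model for score decile and for characteristics that still differ after matching.

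**The concern.** The design mixes patients starting two drugs together with patients stepping up after single-drug treatment, so disease and treatment duration vary by construction. Duration plausibly bears both on which second drug is chosen and on the risk of exacerbation and pneumonia. Section 7.11 ranks confounding by indication among the main threats, and 7.6 answers it by relying on matched patients being equally likely to receive either combination. A one-year window does not secure that for a factor that builds up over many years. At stake is avoidable residual confounding in the primary hazard ratio, the exacerbation rate ratio and the pneumonia hazard ratio.

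**Working it through.** The plan states no figure on this point, so there is none to reproduce. The check sets the sections against each other and uses the plan's own dates.

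**Inputs.** Diagnosis from 1 January 1995 and qualifying prescriptions from 1 January 2002 to 31 December 2015 (7.3). New combined use up to December 2015 (abstract, main inclusion criteria).

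**1. Time since COPD diagnosis.** The maximum is 31 December 2015 minus 1 January 1995, or 21.0 years; the minimum is about 0. Matching on calendar years does not limit the gap closely, because diagnosis precedes base-cohort entry by an unrestricted interval:

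- Both patients enter the base and study cohorts in 2002: one may have been diagnosed on 1 January 1995 and the other just before entry, a gap of up to 8.0 years.
- Both enter in 2015: the gap can be up to 21.0 years.

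**2. Can another element bring diagnosis date in?**

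- *Score data:* a COPD code in the baseline year may mark a recent diagnosis, but the window cannot separate 3 years from 15.
- *Prior treatment:* this is a class, not a duration. New use is judged on the baseline year and 7.3 gives no other lookback for the class, so someone treated years ago but not in that year could be classed with the never-treated.
- *Severity (7.6):* not defined there; the severity measures in 7.4.3 cover one year.
- *Adjustment after matching (7.9.1):* this depends on a characteristic being compared, and duration is on no list of those to compare.

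**3. Time since base-cohort entry.** The result depends on which year is matched:

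| Reading | Largest possible within-pair gap |
|---|---|
| A. Base-cohort entry year only (7.3) | 14.0 years in the 2002 set; 11.0 in 2005; 6.0 in 2010; 2.0 in 2014 |
| B. Cohort-entry year only (one reading of 7.4.3) | 14.0 years for 2015 entrants |
| C. Both years | under 1 year from each date, so under 2.0 years |

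Under A, each figure is 31 December 2015 minus 1 January of the set year. Under B, it is 31 December 2015 minus 1 January 2002. In addition, if the Cox score's time axis runs from base-cohort entry, the score conditions on this time whichever reading applies. The axis is not stated.

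All of these are bounds on what the rules permit. The documents give no distribution of duration from which to compute an expected imbalance.

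**The case against.** **Treatment duration.** A reader might infer that it cannot enter the matching at all. The documents do not support that. The set year in 7.3 is itself a treatment-start anchor, 7.4.3 adds cohort-entry year, 7.6 lists calendar time among the matched factors, and a Cox score may condition on time since base-cohort entry. The design is referred to a cited methods paper that may settle the axis but is not part of the documents. What is left is an unresolved difference between sections, not a proven omission.

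**Age.** It is named only as an entry criterion, and a reader might infer that it is left out of the analysis. But the list in 7.4.3 is expressly a set of highlights, age needs no lookback, and it would ordinarily appear among the baseline characteristics compared under 7.9.1. It needs confirming, no more.

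**Severity control.** Prior class, exacerbation history (with the last 30 days separated), respiratory drugs, antibiotics and study-drug counts all carry some information about disease stage. After conditioning on them, the remaining effect of duration could be small. This is fair and limits how strongly the point can be put, but none of these measures grades duration.

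**Size.** A reader might also infer a bias as large as the smallest effect considered in 7.7, HR 0.90. That needs two assumptions: for example, a hazard rising 3% to 8% per year of duration and arms differing by 1 to 2 years gives factors from 1.03 to 1.08² = 1.17. Neither assumption has support in the documents, and no direction is established.

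**Conclusion.** As written, time since first recorded COPD diagnosis is outside the matching, the score and the listed outcome-model covariates. The stated one-year rule keeps it out, so this goes beyond a detail left unwritten. Pairs may differ by up to about 21 years, and matching on both calendar years would not close the gap. Time since base-cohort entry is controlled if both years are matched (under 2 years) or if the score's time axis starts at base-cohort entry; with a single year and another axis the gap can reach 14 years, and the plan does not say which applies.

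The conclusion rests on reading the one-year window literally and on the plan's date limits. That duration confounds the comparison is plausible rather than shown. The point is worth acting on before the analysis because it touches the study's main threat to validity and costs little.

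**What to change.** 1. Reconcile 7.3 and 7.4.3 on which calendar year or years define the exposure sets, and state the time axis of the Cox score.
2. Exempt duration from the one-year lookback. Add time since first recorded COPD diagnosis to the score and to the Cox and negative binomial models. Add time since base-cohort entry in the same places unless it is already the score's time axis.
3. Confirm in 7.4.3 that age at cohort entry is included.
4. Report balance on all three, before and after matching.

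**Cost.** The dates are already needed to build the base cohort, so the work is a few derived variables and a short text change. There are limits. Only one year of up-to-standard history is required, so first recorded diagnosis may reflect registration rather than onset. Base-cohort entry counts prescriptions only from 2002, although 7.3 dates LABAs to the 1990s, so it understates treatment duration for some patients. New score terms may change which pairs fall within the 0.05 caliper; the effect on the expected 3,000 per arm cannot be computed from the documents, though the closest-match fallback means that missing the caliper does not by itself exclude a patient.
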